- Hyp 1:** The intervention will be feasible and acceptable as evidenced by high rates of recruitment, adolescents' high adherence to the treatment protocol, and their high satisfaction ratings of the intervention.
- Hyp 2:** Over 2.5 months post-treatment, relative to controls, adolescents randomized to our innovative sleep intervention will have improvement on two **primary sleep quality outcomes** – (a) sleep duration and (b) sleep fragmentation (i.e., sleep efficiency and disruptions) – measured objectively (actigraphs) and subjectively (Core Consensus Sleep Diary [CSD]²² and the Pittsburgh Sleep Quality Index [PSQI]^{23,24}).

To accomplish these aims, this study includes two phases.

Phase 1: Development Phase. We will develop the intervention using a participatory design with input from adolescents, sleep experts, and SBHC providers and staff;

Phase 2: Pilot Individually Randomized Group Treatment Trial (IRGT). We will enroll 60 adolescents from two high SBHCs in New York City whose typical sleep duration is below what is recommended for this age group. Adolescents within each SBHC will be randomized to one of two study arms: (1) the *Sleeping Healthy/Living Healthy* intervention or (2) an attention control consisting of health education including sleep hygiene in adolescents. We will follow adolescents for 2.5 months post-intervention.

Background/ Rationale

Poor sleep quality – characterized by insufficient sleep duration, disrupted sleep, and difficulty falling asleep – in urban adolescents is a growing public health concern.²⁵⁻³¹ Sleep is critical for healthy development. While adolescents have a greater need for sleep than pre-pubertal children, poor sleep hygiene, shorter sleep duration, and poor sleep quality, including sleep disruptions, are particularly prevalent among adolescents in general²⁵⁻³⁶ – and more specifically urban adolescents.³⁷⁻³⁹ Poor sleep is associated with increased risk-taking, poor academic performance, and impaired psychological and physical health.^{31,40-57}

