Baseline	Sleep actigraphy (2 weeks)	During intervention (7 weeks)	Post-intervention	Sleep actigraphy (2 weeks)	Follow-Up (2.5 months post intervention)	Sleep actigraphy (2 weeks)	Measure	Construct	# of items	During...	Time duration	Notes
X							Participant demographics	Age, gender, grade, school, race, ethnicity	6	N/A	5 mins	
X							General Sleep Inventory (GSI)	Sleep location	10	Current	<5min	In baseline survey
	X		X		X		Actigraphy	Sleep duration, sleep onset latency, sleep efficiency				Participants wear actigraph for 2 weeks, return actigraph for data download and charging
	X			X		X	Core Consensus Sleep Diary (CSD)	Sleep duration; sleep fragmentation; subjective sleep quality	9	Daily	2-5 mins	
		X					National Youth Physical Activity Survey (NYPANS)	Daily physical activity (total Q8; vigorous Q10) in previous day	2	Daily	1 min	Control group only
X			X		X		Pittsburgh Sleep Quality Index (PSQI)	Sleep duration; sleep fragmentation	18	Last month	~5-15min	Omitted Q10
X			X		X		Adolescent Sleep Hygiene Scale (ASHS)	Sleep hygiene	33	Last month	~5min	
X			X		X		Perceived Stress Scale (PSS-14)	Stress	14	Last month	<5min	
X			X		X		PROMIS Ped Psychological Stress Experiences 8a	Stress	8	Last 7 days	<5min	
X			X		X		PROMIS Ped Anxiety 8a	Anxiety	8	Last 7 days	<5min	
X			X		X		PROMIS Ped Sleep 8a	Sleep-related impairment	8	Last 7 days	<5min	
X			X		X		MAAS-A	Mindfulness	14	Last 7 days	<5min	
			X				Participant Experience Survey – Part 1	Contamination, satisfaction, self efficacy				
			X		X		Participant Experience Survey – Part 2	Use of skills in last week				Treatment group only

3. Study Procedures

PHASE 1 – Development Phase

To develop *Sleeping Healthy/Living Healthy*, the PIs will use a 4-step iterative process.

Step 1: Identify Salient Intervention Components. We will initially identify salient intervention components four ways.

(1) The investigative team will update our literature review and review published sleep hygiene interventions to ensure we have the most relevant potential intervention components.

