Randomization. We will enroll 60 adolescents from two SBHCs in NYC (n=30 per SBHC). Within each school, we will randomize participants in equal numbers to the treatment (n=30) or control (n=30) group using urn randomization techniques¹³⁹⁻¹⁴¹. Participants will be randomized within each SBHC (2 arms x 2 SBHCs x 2 cohorts) in equal numbers to receive either the intervention or an attention control condition. Randomization of each participant will occur when the participant completes the baseline assessments. The urn randomization algorithm will be implemented using SAS 9.3 (SAS institute, 2002) by our biostatistician. This procedure conceals allocation to treatment or control from participants and study staff until just before the intervention begins. Sex and sleep duration at baseline will factor into the urn randomization procedure, making it more likely that groups will be balanced on these variables.

We will minimize contamination [using procedures used in our prior trials]: (1) train half the providers in each SBHC to deliver the intervention, allowing control participants to be seen by the other providers; (2) encourage control providers to not address sleep above and beyond what they would normally do when seeing non-intervention patients; [(3) ask treatment providers to not share the intervention content or materials with colleagues]; and (4) emphasize to the adolescents the importance of minimizing discussion of intervention content beyond the intervention setting.

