Intervention Training and Fidelity. Providers at each SBHC will deliver the *Sleeping Healthy/Living Healthy* because we are creating a dissemination model leveraging existing resources. Drs. [name] and [name] have each trained providers to deliver interventions.¹⁴²⁻¹⁴⁶ To ensure consistency in training across SBHCs, we will use identical training procedures for each SBHC using a structured training curriculum [adapted from our prior research]. We will employ established procedures to minimize interventionist effect. Drs. [name] and [name] will provide training and lead bi-weekly supervision meetings. Group intervention and control sessions will be audio recorded; a trained study staff member will review each tape and complete a Fidelity Checklist based on Borrelli’s framework.¹²⁶ Because recording the individual sessions has the potential to interfere with provider-participant rapport, to assess fidelity of these sessions, immediately after each individual session, each provider will complete a Fidelity Checklist. For all Fidelity Checklists, a fidelity score is generated by dividing the number of covered elements by the total number of session elements; fidelity scores below 85% will trigger discussion in supervision meetings. [Fidelity Checklists will be examined for contamination, retraining providers as needed.]

Data Collection. Blinded trained study staff will interview adolescents three times: (1) baseline; (2) immediate post-intervention; and (3) 2.5-month follow-up. Interviews will take place at school or via telephone/Zoom during the school day; telephone interviews and/or online surveys will be utilized as needed to capture chronically absent students. Adolescents will wear the actigraphs for two weeks prior to each interview with actigraphy data being downloaded during the interview. The formative process evaluation includes immediate post-intervention interviews with the adolescents and SBHC providers and staff to obtain feedback regarding intervention procedures.

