Implementation. *Sleeping Healthy/Living Healthy* (treatment) and *Sleep for Teens* (control) will run concurrently in two waves: one wave during the fall semester and a second wave in the spring semester. Both *Sleeping Healthy/Living Healthy* and *Sleep for Teens* will consist of five group sessions and two individual sessions delivered once a week over the course of seven weeks (see Table 2 below and “Sample Sleeping Healthy/Living Healthy Group Manual” attached). Sessions will be delivered in person at the SBHC or school, or remotely via Zoom. Each group will consist of 7-8 adolescent participants. *Sleeping Healthy/Living Healthy* will be implemented by two SBHC staff per group, with the same staff conducting individual sessions to build facilitator-participant rapport. *Sleep for Teens* will be run by non-SBHC staff. All group and individual sessions will be audio recorded using a secure Zoom account or a password-protected device to monitor fidelity. Recordings will be transmitted to authorized study personnel via encrypted message, and will be destroyed once fidelity checklists are completed.

Table 2. Treatment and Control Pilot Implementation

				FALL		FALL		SPRING		SPRING	
		Wave>		Wave 1A		Wave 1B		Wave 2A		Wave 2B	
		School>		GW	GW	IS 52	IS 52	GW	GW	IS 52	IS 52
		Implementer>		SBHC staff	Non-SBHC staff	SBHC staff	Non-SBHC staff	SBHC staff	Non-SBHC staff	TBD	Non-SBHC staff
		Arm>		Treatment	Control	Treatment	Control	Treatment	Control	Treatment	Control
Week		Duration	Intervention Topics	Control Topics							
1	Group 1	40m	Sleep basics, mindful breathing	Importance of sleep for health	1 group						
2	Group 2	40m	Good sleep practices, acupressure	Stress management	1 group						
3	1:1	20m	Review of sleep data & use of techniques, problem solve	Review of stress management techniques	7-8 meetings						
4	Group 3	40m	Sleep routines, tapping	Nutrition & physical activity	1 group						
5	1:1	20m	Review/problem solve, teach body awareness	Review of nutrition and physical activity	7-8 meetings						
6	Group 4	40m	Sleep environment & mindful attention	Time management	1 group						
7	Group 5	40m	Wrap up & celebration	Wrap up & celebration	1 group						

Notes: 8 x 7.5 participants = N of 60

Control topics: didactic content on importance of healthy sleep, stress management, nutrition, exercise, time management

Control sessions will be held at SBHC locations but will not be conducted by SBHC staff or providers

Compensation.

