Adolescent Participants. We will enroll 60 adolescents in grades 9 – 11 with poor sleep from two SBHCs in NYC (n=30 per SBHC). Based on SBHC data [and our prior trials], we anticipate 50% will be female, and 86% will be racial/ethnic minorities (68% Hispanic; 28% Black, not mutually exclusive). Inclusion criteria include being between the ages of 13 and 17.9, patients enrolled in one of the SBHCs, in grades 9 – 11, and reporting sleep duration <8 hours (below the recommended number of hours of sleep for this age group^{127, 128}) using the following questions: What time do you: (a) usually fall asleep on weekdays and (b) usually wake up on weekdays? Exclusion criteria: Report of prior diagnosis of a sleep disorder (e.g., sleep disordered breathing, restless leg syndrome); significant developmental delay and/or severe psychiatric or medical conditions that preclude completion of study procedures or confound analyses; or not be able to communicate in English.

5. Recruitment

PHASE 1 – Development Phase

Recruitment of adolescent participants: Teen Advisors (n=2);

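### The baseline-to-follow-up sequence is about as long as a semester or longer, so spring-wave follow-up may fall after the school year, and the analysis plan allows for neither wave nor school nights

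*Combined protocol and SAP*

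**What the plan says.** Section 3 (Phase 2, Implementation) has treatment and control running concurrently in two waves, "one wave during the fall semester and a second wave in the spring semester". Each programme is "five group sessions and two individual sessions delivered once a week over the course of seven weeks". Table 2 places four of its eight groups in spring. No start dates, end dates or semester length are given.

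On the sequence around the sessions:

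- Baseline comes before allocation: "Randomization of each participant will occur when the participant completes the baseline assessments" (section 3, Randomization).
- Section 1 states "We will follow adolescents for 2.5 months post-intervention".
- Section 3, Data Collection, states "Adolescents will wear the actigraphs for two weeks prior to each interview with actigraphy data being downloaded during the interview".
- Table 1, by contrast, lists a two-week actigraphy column after each of baseline, post-intervention and follow-up.
- Data Collection also says "Interviews will take place at school or via telephone/Zoom during the school day".

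Eligibility (section 4, Phase 2) requires reported sleep under 8 hours, worked out from when the adolescent usually falls asleep on weekdays and when they "usually wake up on weekdays". Randomization is within health center and cohort. The Statistical Analysis text in section 2 names neither wave nor health center as a covariate, and it does not separate school nights from other nights.

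**The concern.** The trial recruits adolescents who report short sleep on weekdays, and it measures them for two weeks at a time at three points. If the last recording falls after the school year for one wave, the conditions under which sleep is measured differ between waves, and differ from those at baseline. Hypothesis 2 concerns the 2.5 months after treatment, and section 2 says Phase 2 is meant to supply potential effect sizes for a larger trial. The reader of that estimate needs to know whether it describes term-time sleep, vacation sleep or a mixture. A shift between waves that the analysis ignores also adds noise to a sample of only 60.

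**Working it through.** **Inputs from the documents.** Baseline actigraphy 2 weeks; sessions 5 + 2 = 7 weeks; follow-up interval 2.5 months; N = 8 × 7.5 = 60, matching the note to Table 2. Spring share: 4/8 × 60 = 30. The Study Purpose in section 1 still anticipates two group and two individual weekly sessions. The Phase 2 design text, Table 1, Implementation and Table 2 all give seven weeks, so seven is used here.

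**Assumed.** Semester length of 18 to 22 weeks, and seasonal shifts of 0.5 and 1.0 SD. The documents give neither.

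**Length of the sequence.** 2.5 months = 2.5 × 365.25 / 12 / 7 = 10.9 weeks.

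- Actigraphy before each interview (Data Collection): 2 + 7 + 10.9 = 19.9 weeks.
- One further two-week block, either after the post-intervention assessment or after follow-up: 21.9 weeks.
- Table 1 columns read fully in sequence: 2 + 7 + 2 + 10.9 + 2 = 23.9 weeks.

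**Slack at the end of term** (semester length minus the end of the follow-up recording, for semesters of 18 to 22 weeks):

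| Reading | Baseline starts in semester week 1 | Session 1 in week 1, baseline done earlier |
|---|---|---|
| 19.9 weeks | −1.9 to +2.1 | +0.1 to +4.1 |
| 21.9 weeks | −3.9 to +0.1 | −1.9 to +2.1 |
| 23.9 weeks | −5.9 to −1.9 | −3.9 to +0.1 |

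Each week spent on recruitment, on filling groups or on a recess is a week off these figures. The right-hand column moves the baseline recording ahead of the semester. Baseline may then include non-school nights, and baseline sleep duration is one of the urn randomization factors.

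**Effect on the arm comparison.** Treatment and control share the calendar within each wave and are allocated in equal numbers within health center and cohort. A seasonal shift common to both arms therefore cancels in the difference, and there is no bias.

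**Effect on precision.** Suppose half of each arm is shifted by s SD at follow-up. The variance of the outcome within an arm, ignoring wave, is then 1 + s²/4 times the variance within a wave.

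- s = 0.5: 1 + 0.25/4 = 1.06. Sixty participants then give the precision of 60/1.0625, about 56.
- s = 1.0: 1 + 1/4 = 1.25. Sixty give the precision of 60/1.25 = 48.

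A wave term in the model removes this excess. Adjustment for the baseline value does not, because the shift arises after baseline.

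**What a wave-by-arm estimate could show.** With about 15 per arm per wave, the standard error of the interaction is √(4/15) = 0.52 SD, giving a 95% interval of about ±1.0 SD even before clustering within treatment groups is allowed for.

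**School nights.** Two weeks contain 10 school nights and 4 weekend nights. A gain confined to school nights would appear in the all-night mean at 10/14 = 71% of its size, so the two summaries can differ even when every recording is in term.

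**The case against.** The strongest reply is that the calendar is not in the documents. The semester phrase describes when the programmes run; it does not say that baseline and follow-up share the same semester. Planning interviews for the school day suggests that follow-up in term was intended. The Data Collection text is also a firmer basis than the column order of a table that may have been damaged in extraction, and it gives the shortest sequence. With an early start, follow-up can stay in term. This stands, and it is why the point is put as a risk. A reader might infer that spring follow-up will probably record vacation sleep, but the documents do not support that. They equally do not establish where the fall-wave recording falls. What the reply lacks is any schedule that secures the intention.

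A reader might also infer that the 2.5-month effect is diluted, perhaps to half, which would call for 1/0.5² = 4 times the sample. That needs every spring recording to fall in vacation and the effect there to be zero. If the effect is the same in both seasons there is no dilution. Nothing in the documents establishes an arm-by-season interaction, or its direction.

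Nor do the documents make school nights the only proper outcome. The weekday question is a screening item. The outcomes are duration and fragmentation, by actigraphy, diary and PSQI, and an all-night mean is a legitimate target.

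Finally, feasibility is the stated primary goal, and the immediate post-intervention assessment, about 9 to 11 weeks after a day-one start, would give a term-time estimate from the whole sample. This is a useful fallback, but it does not answer the hypothesis about 2.5 months.

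**Conclusion.** The point holds as a gap in scheduling and analysis, and not as a bias. The sequence takes about 20 weeks on the Data Collection reading and 22 to 24 on the Table 1 order. Over an assumed semester of 18 to 22 weeks, with baseline starting in week 1, that leaves between 2.1 weeks to spare and 5.9 weeks of overrun. About 30 of 60 participants are exposed to this risk.

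If the overrun happens, three consequences follow. The pooled 2.5-month estimate mixes term and vacation conditions. Change from baseline within an arm cannot be separated from season. Unadjusted variance rises by 6% to 25% for an assumed shift of 0.5 to 1.0 SD, and not at all if there is no shift. The size and direction of any change in the treatment effect itself cannot be worked out from the documents.

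**What to change.** 1. Include wave (cohort) and health center, the groups within which participants are randomized, as covariates in the outcome analysis. With two waves and two centers the cost is two degrees of freedom.
2. State the wave dates, and set the spring dates so that the two-week follow-up recording ends before the last school day. Record any exceptions with their dates. This is also the only step that helps the PSQI, which asks about the last month and cannot be split by night. Keep the 2.5-month interval in both waves; shortening it in spring would create a new difference between waves.
3. Label each actigraphy and diary night as school or non-school, in both waves, and report the school-night mean beside the all-night mean. The school-night summary rests on about 10 of 14 nights.
4. Reconcile Data Collection with Table 1 on whether actigraphy precedes or follows each assessment. This alone moves the end of follow-up by 2 to 4 weeks.

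Any wave-by-arm result should be presented as descriptive only. Beyond calendar planning, the cost is a few sentences in the analysis plan and a night label applied to data already being collected.

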Adolescent Control and Intervention Participants (n=60). As in Phase 1, participants will be recruited through the SBHC communication channels and through the Teen Advisors. Flyers will be provided to SBHC providers and staff to share with patients in person, through their telehealth visits with patients, or via secure message sent by the treating physician through EPIC, the SBHCs' electronic health record system. In the secure message, the treating physician will ask the patient for permission to be contacted by the Research Coordinator, and will also provide the Research Coordinator's contact information if the patient wants to learn more about the study. Study team members will be onsite at the SBHCs to distribute flyers to patients, describe the study, and ask interested patients for their permission to be contacted by the Research Coordinator about the study. Flyers will also be posted in the SBHCs and throughout the school where permitted. All recruitment materials will specify that the study is only open to registered SBHC patients.

Adolescents who are interested in participating in the program will be provided with the CUIMC email address and cell phone number for the study staff (Research Coordinator) to learn more about the project, and to conduct initial eligibility screening. Given the current COVID-19 situation, we are seeking a waiver of written informed consent for Phase 2 procedures as we did in Phase 1 to allow for the possibility that NYC schools move to remote learning. In this case, participants may not be seen in-person so having to print, sign, and send written consent forms increases the risk of a breach of confidentiality. The study staff will use an Information Sheet script to describe the study components and the features of participation (included in documents) and solicit informed consent, which will be documented by study staff.

Eligibility Screening - Adolescent Control and Intervention Participants – Trained study staff will screen adolescents for eligibility for the program detailed above in Section 4. To screen participants, trained study staff will ask adolescents: 1) if they would like to determine their eligibility to participate in a study; 2) if so, their age; 3) grade; 4) whether they are enrolled in the SBHC; and 5) what time they: (a) usually fall asleep on weekdays and (b) usually wake up on weekdays.

6. Informed Consent Process

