All Informed Consent procedures will start with a concise presentation, in lay language, of the key information about the research study. Sufficient information about the study purpose, procedures, risks, and benefits will be provided to all potential subjects. All potential subjects will have an opportunity to discuss the information provided.

Adolescent Participants. All adolescent participants are expected to be able to provide assent to participate, as they are currently enrolled students in high school and English speaking. Trained study staff will use structured oral scripts (information sheet) to describe the study to eligible patients, review the elements of informed consent to obtain assent, and describe the process for contacting the parent/guardian for parental consent. The materials will explain that the SBHC is conducting a study to improve adolescents' sleep, and will include contact information for the study team so that parents/guardians will be given the opportunity to call the investigators to have any questions answered or concerns addressed. The informed consent (for adults)/assent (for the SBHC patients age <18) forms provided will explain, in plain language written at no higher than 8th grade reading level, who is conducting the study, the purpose of the study, the procedures (including the length of focus groups and program sessions and the number of assessments and surveys), study risks and benefits, a discussion of compensation, and a statement that participation is voluntary and their participation will not affect their care at the SBHC. Because a written signature would serve as a source of identification that introduces risk, following reading of the informed consent information sheet, the trained study staff will obtain verbal consent from the participant prior to the date of the focus group for Step 1 and Step 3, first meeting for Teen Advisors, and baseline assessment for Phase 2 participants. All oral explanations and verbal consent forms will be IRB and HIPAA compliant. Informed consent forms for the Phase 2 trial will include mention that the study is registered with the ClinicalTrials.gov website.

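### Does the Phase 2 screening list leave the sleep-disorder and medical exclusions unchecked before randomization?

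*Combined protocol and SAP*

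**What the plan says.** Section 4 (Study Subjects, Phase 2) gives four inclusion criteria: age 13 to 17.9, enrolment as a patient at one of the school-based health centers (SBHCs), grades 9 to 11, and reported sleep under 8 hours. It gives three exclusions. The first is "Report of prior diagnosis of a sleep disorder (e.g., sleep disordered breathing, restless leg syndrome" (the parenthesis closes there). The second is significant developmental delay and/or "severe psychiatric or medical conditions that preclude completion of study procedures or confound analyses". The third is inability to communicate in English.

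Section 5 (Recruitment, Phase 2, Eligibility Screening) begins with a general commitment: "Trained study staff will screen adolescents for eligibility for the program detailed above in Section 4". It then numbers five questions: willingness to be screened, age, grade, and finally "4) whether they are enrolled in the SBHC; and 5) what time they: (a) usually fall asleep on weekdays", with the wake time as part (b). The recruitment text just before it describes this contact as initial screening.

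Three later steps come before allocation:
- **Assent (Section 6).** Staff "describe the study to eligible patients, review the elements of informed consent to obtain assent".
- **Baseline (Table 1).** The demographic items are "Age, gender, grade, school, race, ethnicity".
- **Randomization (Section 3).** "Randomization of each participant will occur when the participant completes the baseline assessments".

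**The concern.** An exclusion that depends on a report works only if someone asks for the report. The numbered list looks like the screening procedure, and it contains no such question. The assent text speaks of patients already found eligible, no baseline construct in Table 1 is a diagnosis or medical history, and randomization follows baseline with no eligibility confirmation mentioned. For the second exclusion, the documents do not say who judges it or from what information.

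A treating provider might know the history, but an adolescent can enter without passing through one. Teen Advisors help recruit, and "Flyers will also be posted in the SBHCs and throughout the school where permitted".

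Read literally, the list would let adolescents with a diagnosed sleep disorder be randomized into a trial whose primary outcomes are sleep duration and fragmentation. They would remain in the intent-to-treat analysis. They would also count as eligible in the eligibility rates and reasons reviewed weekly under Section 11, which a later full-scale trial might use for planning.

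**Working it through.** The plan states no figure to reproduce here. The check sets each Phase 2 criterion in Section 4 against the questions listed in Section 5.

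| Section 4 criterion | Listed question in Section 5 |
|---|---|
| Age 13 to 17.9 | Item 2 |
| Grades 9 to 11 | Item 3 |
| SBHC patient | Item 4 |
| Sleep under 8 hours | Item 5 |
| Exclusion: reported sleep-disorder diagnosis | None |
| Exclusion: developmental, psychiatric or medical condition | None |
| Exclusion: cannot communicate in English | None, but evident in an oral screen |

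Item 1 is willingness. All four inclusion criteria are matched. Two exclusions have no listed question, so the observation about the text is correct.

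**Is the list meant to be complete?** Three points suggest it is not.
1. It follows a sentence that commits staff to Section 4 eligibility as a whole, and Section 4 includes the exclusions.
2. The two Phase 1 lists in Section 5 (Teen Advisors and focus groups) ask about willingness, age, grade and SBHC enrolment. They also omit every exclusion, although Section 4 sets the same exclusions for those groups. The Phase 2 list adds one item, and it is the one new inclusion criterion. All three lists therefore look like inclusion items written out, with the exclusions left to Section 4.
3. The contact is called initial, and Section 11 has ineligibility reasons reported weekly, so reasons are recorded somewhere.

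**Could baseline fill the gap?** Table 1 cannot settle this. It names constructs and does not show item wording; the 10-item General Sleep Inventory, for example, appears only under sleep location. The absence of a diagnosis label is weak evidence either way.

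**Can a lapse bias the comparison?** Screening precedes baseline, and baseline precedes allocation. A missed exclusion cannot depend on arm, and anyone wrongly included is assigned by the same urn procedure as everyone else.

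**How many could be affected?** Let p be the share of otherwise eligible adolescents who would report a diagnosis. The documents give no value, so 1%, 3% and 5% are assumptions, as is the absence of any other route that removes these adolescents. With n = 60:

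- Expected number, 60p: 0.6, 1.8, 3.0.
- Chance of at least one, 1 − (1 − p)^60: 45.3%, 83.9%, 95.4%.
- Relative overstatement of the eligibility rate, 1/(1 − p) − 1: 1.0%, 3.1%, 5.3%.

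The chance of at least one looks large only because 60 people are counted; the expected number stays between 0.6 and 3.0. These figures bound what would follow if nobody asked. They are not evidence that nobody will ask.

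**The case for a change.** The strongest reply is that a commitment to Section 4 shows intent but not method, and the only sentence that gives the method leaves these exclusions out. The Phase 2 list was visibly adapted from Phase 1, so its author had the chance to add them. For SBHC staff, who have no exclusion criteria, Section 5 says eligibility is confirmed before the interview; no such sentence exists for the randomized adolescents, who do have exclusions. Record access in Section 8 is limited to recruitment by the treating provider and is not described as an exclusion check. The principal investigators' interview is for Teen Advisor candidates only.

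All of that is accurate. It establishes that the text does not say where the diagnosis report is obtained. It does not establish that the report goes unasked, because the screening form is not supplied and the general commitment covers the exclusions.

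The part about the second exclusion is weaker. A criterion framed as whether a condition would prevent completion or confound the analysis is an investigator's judgement. Leaving the assessor unnamed in a minimal-risk pilot is a matter of how much detail one prefers, and no contradiction or specific consequence can be shown from it.

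**Conclusion.** No change to the plan follows. The Section 5 list is shorter than Section 4, but this is a gap that staff can fill sensibly: they are told to apply Section 4, and its first exclusion, worded as a report, already points to asking the adolescent.

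Even if the question were missed, no bias between arms would follow, because any lapse precedes allocation. No effect on the sleep outcomes can be computed from the documents. Under the assumed prevalences of 1% to 5%, the expected number affected is 0.6 to 3.0 of 60, and the eligibility rate would be overstated by a relative 1.0% to 5.3%. Section 2 makes design feasibility the primary goal, and shifts of that size would not overturn a conclusion about whether the pilot can recruit and deliver its sessions.

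This conclusion assumes that staff apply Section 4 as Section 5 instructs them to. The screening form, which the documents do not include, would confirm or refute that.
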